Estimates from the literature were used to calculate the sample size needed for this study for the outcomes of changes from month 0 to month 5 in our primary outcome, heart failure quality-of-life. We assumed that the standard deviations (SD) seen in the current study would be similar to that in a similar study conducted in an urban setting in the United States.¹³ Sample size calculation were based assuming 80% power for a two-sided test at alpha of 0.05, and SD of 20.0. With the outcome of change in heart failure quality of life score from baseline to 5 months, considering as a minimum clinical difference of 10 points in the heart failure quality of life score, the sample size

needed was 63 individuals in each arm. We assumed a retention in the current study of 80%, thus the sample size needed at recruitment was at least 158 (n=79 in each arm)

8) Framework

The superiority hypothesis testing framework will be used, testing whether exposure to the intervention results in better outcomes than exposure to the control standard of care. Comparisons will be presented as differences between arms in changes in outcomes from baseline to 1 month to capture changes in acute heart failure symptoms and 30-day readmission; and from baseline to 5 months of follow-up to capture longer term and potentially sustained benefits.

9) Statistical interim analyses and stopping guidance

- a. Information in interim analyses specifying what interim analyses will be carried out and listing time points
 - i. None planned
- b. Any planned adjustment of the significance level due to interim analysis
 - i. No
- c. Details of guidelines for stopping the trial early
 - i. None

10) Timing of final analyses

Final analyses will begin in Fall 2021 upon completion of all field data collection in Fall 2020 and completion of all medical record data collection (Summer 2021).

11) Timing of outcome assessments

Research staff administered full surveys to both arms at baseline, 1 month, and 5 months. Additional brief surveys were collected at months 2 and 3. Medical record data were collected continuously in both arms from 3 months prior to baseline until 9 months after baseline.

Section 4: Statistical Principles

12) Level of statistical significance

95% confidence intervals and exact p-values (or $p<0.001$) will be reported.

13) Description and rationale for any adjustment for multiplicity and, if so, detailing how the type I error is to be controlled.

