2. Patients with six or more hospital admissions within the last twelve months
3. Patients who are being discharged to a living facility that provides meals to residents.

4. Patients who anticipate moving from their current housing situation to one that does not meet our inclusion criteria within six months of enrollment.
5. Patients who are part of meal provision program that provides more than 7 meals a week to the patient.
6. Patients who are unable to feed themselves and do not have adequate support to help them with feeding.
7. Patients with limited physical, cognitive, or behavioral abilities that would interfere with their ability to follow-up with a study as determined by their ability to receive the Project Open Hand services and follow up with survey interviews
8. Patients with anticipated life expectancy of less than a year.
9. Patients who lack capacity to consent to a research study.
10. Patients currently requiring dialysis or determined to need dialysis in the next 6 months.
11. Patients with severe allergies to eggs, soy, wheat, nuts, seeds, seed oils, pineapple, raisins, or certain vegetables such as onions (allergies are considered on a case-by-case basis in consultation with Project Open Hand).

19) **Recruitment** – A CONSORT flow diagram will be used to summarize the number of participants who were:

- a. Assessed for eligibility at screening
 - i. Among people with heart failure, 2996 people were assessed for eligibility
 1. 2451 did not meet the inclusion criteria
 2. 127 Discharged before doing the baseline evaluations
 3. 226 were not interested in participating in the study
 - ii. Eligible and randomized
 1. 192 were eligible and randomized
 - a. 106 allocated in the intervention arm
 - i. 27 were early withdrawals
 - b. 86 allocated in the control arm
 - i. 4 were early withdrawals

See CONSORT diagram for detail on reasons for ineligibility

20) Withdrawal/follow-up

Reasons and details of withdrawal and lost to follow up at month 1 and 5 for both arms will be reported and summarized in the CONSORT flow diagram.

- a. Level of withdrawal, e.g., from intervention and/or from follow-up
 - i. Participants were withdrawn from the study due to unavailability to immediately reach out by phone, not meeting the eligibility criteria or deceased immediately following the randomization.

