 1. 16 (15.1%) of randomized intervention and 2 (2.3%) of randomized control participants were unable to be contacted by phone after the baseline evaluations.
 2. 6 (5.7%) participants allocated to the intervention and 2 (2.3%) participants allocated to the control arm were excluded because did not meet eligibility criteria after randomization, and 3 (2.8%) participants in the intervention arm were immediately re-hospitalized.
 3. 1 (0.9%) participant in the intervention arm died after being randomized.
 - ii. Lost to follow up (LTFU) occurred through loss of contact with study participants, moving out of the study area, and death. Intervention participants were also considered LTFU if they withdrew consent. Among

those that were randomized and contacted immediately after randomization (n=79 in intervention arm, and n=82 in control arm):

1. At month 1, 75 (94.9%) of intervention participants and 78 (95.1%) of control participants were retained from month 0.
2. At 5 months of follow-up, 60 (75.9%) of intervention participants and 59 (71.9%) of control participants were retained from month 0.

b. Timing of withdrawal/LTFU data

- i. Intervention participants left the study prior to their first encounter with Project Open Hand were considered withdrawn, otherwise they were considered LTFU.
- ii. Control participants that left the study prior the first call from UCSF staff were considered withdrawn, otherwise they were considered LTFU.
- iii. Participants that were excluded immediately after randomization were also considered early withdrawals.

c. Reasons and details of how withdrawal/LTFU data will be presented

- i. Withdrawal and LTFU data are presented in the CONSORT diagram, stratified by study arm and visit. These data are included to establish lack of bias in screening and retention between the two arms. (See appendix 2)

21) Baseline patient characteristics

We will evaluate several socio-demographic and clinical characteristics at baseline by which we will describe our study sample. These are outlined in Table 1 below and a shell table is provided in the appendix. We will stratify these characteristics by intervention and control arms and report median and the inter-quartile range for continuous variables with skewed data and mean and SD for continuous variables with normal distribution. Categorical variables will be presented as numbers and percentages. No significance testing will be conducted or reported at baseline per CONSORT guidelines.

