Table 1: Baseline characteristics of CaRDS participants

Socio-demographic	Age, current gender, race/ethnicity, household size, relationship status, educational attainment
Economic welfare	Household food insecurity, sources of income, food support sources
Clinical	Heart failure quality of life; general health-related quality of life; medication inventory; blood pressure
Nutrition	Dietary quality; food consumption patterns
Mental Health	Depressive symptoms
Behavioral	Self-reported medication adherence; alcohol use, drug use
Healthcare utilization	Recent hospitalizations, ED visits, doctor visits

Section 6: Analysis

22) **Outcome definitions**

a. Aim 1: Primary Outcomes: Heart failure quality of life: The primary outcome for Aim 1 will be heart failure quality of life, which was assessed using the Kansas City Cardiomyopathy Questionnaire (KCCQ) at baseline, 1 month and 5 months, among all study participants. The Kansas City Cardiomyopathy Questionnaire is a 23-item instrument that quantifies physical function, symptoms (frequency, severity and recent change), social function, self-efficacy and knowledge, and quality of life. An overall summary score can be derived from the physical function, symptom (frequency and severity), social function and quality of life domains. A clinical summary score can be obtained from the symptom frequency and burden domains and the physical limitation domain. Scores are transformed to a range of 0-100, in which higher scores reflect better health status.

For analysis of the primary outcomes, we will compare:

- i. Change in the overall KCCQ scores from baseline to five months, by study arm.
- ii. Change in the overall KCCQ scores from baseline to one month, by study arm.
- iii. Change in the KCCQ clinical summary score from baseline to five months, by study arm,
- iv. Change in the KCCQ clinical summary score from baseline to one month, by study arm,
- v. Change in the overall physical domain KCCQ scores from baseline to five months, by study arm.
- vi. Change in the overall physical domain KCCQ scores from baseline to one month, by study arm.

b. Aim 1: Secondary outcomes:

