- i. Hospitalization and Emergency Department use: As a secondary Aim 1 outcome, self-reported data as well as abstracted medical record data on hospital readmission and Emergency Department use were collected. From the data we will assess the number of times participants were admitted to the hospital from baseline to 1 month and from baseline to five months and the cumulative probability of being hospitalized by study arm. The following outcomes will be reported:

1. Admissions to Zuckerberg San Francisco General Hospital from baseline to 1 month, as determined by medical records. Number of admissions to Zuckerberg San Francisco General Hospital from baseline to 1 month, by study arm, adjusting for baseline values (-3 to 0 months).
2. Admissions to Zuckerberg San Francisco General Hospital from baseline to 5 months, as determined by medical records. Number of admissions to Zuckerberg San Francisco General Hospital from baseline to 5 months, by study arm, adjusting for baseline values (-3 to 0 months).
3. Admissions to any hospital from baseline to 1 month, as determined by ZSFGH medical records and self-report of admission to hospitals other than ZSFGH. Number of admissions to any hospital from baseline to 1 month, by study arm, adjusting for baseline values (-3 to 0 months).
4. Admissions to any hospital from baseline to 5 month, as determined by ZSFGH medical records and self-report of admission to hospitals other

than ZSFGH. Number of admissions to any hospital from baseline to 5 months, by study arm, adjusting for baseline values (-3 to 0 months).

- a. Cumulative probability to be admitted to any hospital from baseline to 5 months by study arm.
- 5. Emergency room utilization at Zuckerberg San Francisco General Hospital from baseline to 1 month, as determined by medical records. Number of admissions to the emergency room at Zuckerberg San Francisco General Hospital from baseline to 1 month, by study arm, adjusting for baseline values (-3 to 0 months).
- 6. Emergency room utilization at Zuckerberg San Francisco General Hospital from baseline to 5 months, as determined by medical records. Number of admissions to the emergency room at Zuckerberg San Francisco General Hospital from baseline to 5 months, by study arm, adjusting for baseline values (-3 to 0 months).

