Any planned subgroup analyses for each outcome including how subgroups are defined: Additional models and statistical interactions (i.e., product terms) will be performed to identify characteristics of individuals who most benefitted from the intervention, such as biological sex, and food insecurity.

24) Missing data

- a. The study team employed several strategies to account for and address missing data during the CaRDS trial period. To prevent or reduce missing data, data collection was computerized, and the questions were obtained through a trained interviewer. The analyst will examine patterns of non-response and inspect distributions of mediating and outcome variables to identify outlying or unusual values and assess distributional characteristics. Missing data will be categorized into: 1) missed individual questions, 2) missing forms, and 3) missed visits.
- b. Missed individual questions: Multiple imputation will be used to address incomplete data arising from missing forms. The assumption will be that incomplete data arise from a conditionally missing-at random mechanism (MAR). Auxiliary variables will be included to help meet the MAR assumption and sensitivity analyses will be conducted with weighted multiple imputation to assess the MAR assumption. Information on percent of questions missing and imputed will be reported for each variable as appropriate in study manuscripts. Missing items from a scale will be imputing using the other items in the scale.
- c. Missed visits: When a participant missed a visit, either home or clinic or both, this was noted in the study register.

25) Additional analyses – None

26) Harms

i. Data safety:

The study team took several proactive strategies to insure the highest levels of data safety. First, data were collected on password protected tablets or laptops. Data were collected using REDCap and stored on a secure UCSF server. The data was stored in a separate folder than other study materials, and only members of the data team had access to this data. Lastly, any individual who requests study data was required to sign a data agreement which included not sharing the data as well as recommendations for data safety. No identifiers have or will be shared with external investigators.

ii. Details on how adverse events are coded or categorized:

Deaths were reported to UCSF by email within 24 hours after the PIs learned of the occurrence. Other adverse events were not reported.

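### No outcome or analysis rule accounts for death, so the KCCQ and utilisation comparisons can be biased, in either direction, if mortality differs by arm

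*Combined protocol and SAP*

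**What the plan says.** **Where deaths are filed.** Section 5, item 20a.ii lists death among the reasons for loss to follow-up: "Lost to follow up (LTFU) occurred through loss of contact with study participants, moving out of the study area, and death". Item 20a.i puts the earliest deaths elsewhere, giving as withdrawal reasons failure to reach the participant by phone and "not meeting the eligibility criteria or deceased immediately following the randomization". The only death stated in the text is of this second kind: "1 (0.9%) participant in the intervention arm died after being randomized".

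**Outcomes.** The first-listed primary comparison in Section 6, item 22a is "Change in the overall KCCQ scores from baseline to five months, by study arm". Utilisation outcomes are counts to fixed horizons, such as "Number of admissions to Zuckerberg San Francisco General Hospital from baseline to 5 months, by study arm", adjusted for the three months before baseline. No primary, secondary, Aim 2 or other outcome is mortality or a composite containing it.

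**Analysis.** Item 16a limits the ITT set to participants with at least one follow-up visit. Section 6 specifies a mixed model over baseline, month 1 and month 5, with ANCOVA as the alternative. A log-rank test is planned for hospitalisation and ED visits, with no rule for participants who die. The missing-data item says only that missed visits were logged, and it does not mention death. Per-outcome sensitivity analyses are marked not applicable, although weighted multiple imputation is mentioned as a check on the missing-at-random assumption.

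**Recording.** Item 26 shows that deaths were notified: "Deaths were reported to UCSF by email within 24 hours after the PIs learned of the occurrence".

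**The concern.** Everyone enrolled had just been admitted with decompensated heart failure, so some deaths within nine months are plausible even though patients expected to live less than a year were excluded. Three mechanisms follow from the plan as written.

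- **Death before month 1.** There is no follow-up visit, so the participant is not in the ITT set.
- **Death between months 1 and 5.** Baseline and month-1 KCCQ stay in the mixed model. The missing month-5 score is handled as if the person were alive and simply not measured. Month-5 ANCOVA drops the participant unless a score is imputed for someone who has died.
- **Death at any time.** No further admissions or ED visits can accrue. The counts to 1, 5 and 9 months take no account of time alive, so an early death lowers the arm's count.

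If deaths are balanced, this matters little. If they are not, the arm with worse survival can look better than it should on both health status and utilisation, and no planned analysis would correct for that.

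**Working it through.** **1. The plan's own figures (item 7).** The inputs are a 10-point difference, SD 20, two-sided 5% and 80% power.
n per arm = 2 × (1.960 + 0.842)² × 20² / 10² = 62.8, so 63. With 80% retention, 63 / 0.80 = 78.75, so 79 per arm and 158 in total. Both stated figures reproduce. The 10 points serve below as a yardstick.

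**2. How much loss could contain deaths (item 20).**

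| | Intervention | Control |
|---|---|---|
| Randomised | 106 | 86 |
| Early withdrawals | 27 | 4 |
| Remaining | 79 | 82 |
| Lost by month 1 | 79 − 75 = 4 | 82 − 78 = 4 |
| Lost by month 5 | 79 − 60 = 19 (24.1%) | 82 − 59 = 23 (28.0%) |
| Lost between months 1 and 5 | 75 − 60 = 15 | 78 − 59 = 19 |

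The text does not say how many of the 19 and 23 died. The CONSORT figure, where this would appear, is not shown in the available copy.

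**3. KCCQ illustration (all inputs assumed except the 60 and 59 retained).** Score a death as 0, let control survivors improve by 10 points, let intervention survivors improve by 10 + g, and let the baseline mean b be 30 to 60.
Intervention mean change = [60 × (10 + g) − d₁ × b] / (60 + d₁). Control mean change = [59 × 10 − d₂ × b] / (59 + d₂), where d₁ and d₂ are deaths.

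Worked case: d₁ = 8, d₂ = 2, g = 0, b = 30. This gives (600 − 240)/68 − (590 − 60)/61 = 5.29 − 8.69 = −3.4.

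| Deaths, intervention v control | Survivors differ by 0: b = 30 to b = 60 | Survivors differ by +10: b = 30 to b = 60 |
|---|---|---|
| 4 v 4 | 0.0 to +0.1 | +9.4 to +9.4 |
| 6 v 2 | −2.3 to −4.1 | +6.8 to +5.0 |
| 8 v 2 | −3.4 to −5.9 | +5.4 to +2.9 |
| 2 v 8 | +3.5 to +6.1 | +13.2 to +15.8 |

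The last row shows the sign reversing when control has the excess. The table sets a survivor mean against a score that includes death. The mixed-model estimate is not the survivor mean, because it also uses month-1 scores from those who later die. The table therefore shows scale; it is not an estimate of bias in the primary analysis.

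**4. Admission-count illustration (all inputs assumed).** Take a constant admission rate while alive, with no treatment effect on it, and 5-month mortality of p₁ v 5%. The admission rate cancels from the ratios.

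(a) *Death unrelated to frailty, constant hazard.* The mean fraction of the period alive is p / −ln(1 − p), and the count ratio is the ratio of these fractions. At 10% v 5%: 0.9491 / 0.9748 = 0.974.

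(b) *Frail patients both die and are admitted more (exponential frailty with mean 1).* The mean count is proportional to 1 − p, so the count ratio is (1 − p₁)/0.95. The mean fraction alive is −ln(1 − p) × (1 − p)/p. Dividing count by time alive gives the ratio after an exposure offset.

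| Mortality | (a) count ratio | (b) count ratio | (b) ratio with time-alive offset |
|---|---|---|---|
| 10% v 5% | 0.974 | 0.947 | 0.974 |
| 15% v 5% | 0.947 | 0.895 | 0.947 |
| 20% v 5% | 0.919 | 0.842 | 0.919 |

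In case (a) the offset restores the ratio to 1. In case (b) it removes only part of the distortion. Simulating the same two models at 0.1 to 0.3 admissions a month gave count ratios of 0.842 to 0.972, in line with these. Under these assumptions the arm with worse survival shows about 3% to 16% fewer admissions with no true effect on the rate.

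**The case against.** The best reply is that deaths are not hidden. Item 20 commits to reporting reasons for withdrawal and loss at months 1 and 5 in both arms, and death is a named reason. A reader might infer that nothing in the plan would reveal a survival difference. The documents do not support that, because deaths by arm should be visible descriptively in the CONSORT diagram. What is missing is any analysis that uses them, and any planned count at 9 months.

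A reader might also infer that anyone who dies drops out of the KCCQ comparison. That is true of deaths before month 1, but later deaths keep their earlier scores in the mixed model. Only 4 per arm were lost by month 1 among those contacted, so in that group the first route is small. Admissions before death, including a final one, still count.

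It is also fair to say that this is a pilot, and that every mortality figure used above is assumed. An 8 v 2 split would need 8 of the 19 intervention losses to be deaths. Total loss is slightly higher in control (23/82 v 19/79).

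These points limit the size and the certainty. None of them supplies a rule for death, and a tally in a flow diagram does not change what the endpoints estimate.

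**Conclusion.** The point holds as a gap in the plan, not as a demonstrated bias. Deaths are split between two administrative categories, and neither the outcomes nor the analyses say what happens to someone who dies. If mortality differs by arm, the KCCQ and utilisation results can be biased in favour of or against the intervention.

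A reader might go further and infer that worse survival under the intervention is being made to look neutral or favourable. The documents do not show this. The single stated death is in the intervention arm, but one early death says nothing about later mortality, and overall loss is higher in control.

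The size is unknown. The illustrations run from nil with equal deaths to about 6 KCCQ points when survivors do not differ (8 v 2 deaths either way, deaths scored 0, baseline mean 30 to 60). That compares with the 10-point minimum difference in item 7. For admissions they run to about 16% (20% v 5% mortality, frailty-linked). A change to the SAP is justified; nothing here invalidates the design.

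**What to change.** 1. **Items 20 and 22: report deaths.** Give known all-cause deaths by randomised arm at 1, 5 and 9 months, separately from other loss and including deaths among the 31 early withdrawals (27 + 4). State for how many of the 192 vital status is known at each time, since the documents do not show that it is held for everyone.
2. **Item 22a: one supporting KCCQ analysis.** Analyse month-5 overall KCCQ by rank, placing deaths before month 5 below all survivors and including deaths before month 1.
3. **Item 22b: supporting utilisation analyses.** For admissions and ED visits, use time alive as exposure, and report beside it a death-or-admission composite, because the offset alone may not be enough when frailer patients die first. Days alive and out of ZSFGH is an option only if lengths of stay were abstracted; the listed outcomes name counts only.
4. **Interpretation.** Say that the KCCQ and utilisation results will be read alongside these analyses. A formal rule blocking a claim of benefit is not advised: without a margin, a chance reversal in a small sample would trigger it.

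**Cost.** SAP wording and a few extra analyses, mostly on records already collected to 9 months, though some death dates may need confirming. The ranked analysis gives no estimate on the KCCQ point scale, and it will change little if deaths are few.

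### Item 20 gives retention only among those left after early withdrawal, and its claim that the data establish lack of bias is contradicted by the SAP's own counts by arm

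*Combined protocol and SAP*

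**What the plan says.** Section 5, item 19 records "106 allocated in the intervention arm", of whom 27 were early withdrawals, and 86 allocated to control, of whom 4 were. Item 20a lists reasons for these losses as percentages of those randomised. It then gives retention only among the 79 and 82 who remained: 75 (94.9%) and 78 (95.1%) at month 1, and at month 5 "60 (75.9%) of intervention participants and 59 (71.9%) of control participants were retained from month 0".

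Item 20b defines early withdrawal by arm. In the intervention arm it means leaving before the first encounter with the food provider; in control, leaving before the first call from study staff. Post-randomisation exclusions also count. Item 20c says the withdrawal and loss-to-follow-up data will appear in the CONSORT diagram by arm and visit, and gives their purpose: "These data are included to establish lack of bias in screening and retention between the two arms".

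Section 3, item 7 sets the planning figures: "Sample size calculation were based assuming 80% power for a two-sided test at alpha of 0.05, and SD of 20.0", with the number evaluable that "needed was 63 individuals in each arm". It continues "We assumed a retention in the current study of 80" percent, so that "the sample size needed at recruitment was at least 158 (n=79 in each arm").

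**The concern.** The printed percentages make retention look equal at month 1 and slightly better in the intervention arm at month 5. They are conditional on surviving a filter applied after randomisation, and that filter removed about a quarter of one arm and under a twentieth of the other.

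The filter also works differently by arm. Item 15 explains that controls could not at first be classed as early withdrawals, and that a call to controls was added later by protocol modification to imitate the provider's call. Item 20a lists three immediate re-hospitalisations and one death among the early losses in the intervention arm and none in control. Readmission is a secondary outcome (Section 6, item 22b), so some of the filtering events are prognostic.

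At stake is what can be concluded about attrition bias. A reader who takes item 20c at its word will treat loss as balanced and will not ask how the comparison might change with the missing participants included.

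**Working it through.** **Inputs.** Randomised 106 and 86; early withdrawals 27 and 4 (item 19). Retained 75 and 78 at month 1, 60 and 59 at month 5 (item 20a). Planning values from item 7: SD 20, difference 10, two-sided alpha 0.05, 80% power, 80% retention.

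**1. Reproduce the printed figures.** 106 − 27 = 79 and 86 − 4 = 82. Month 1: 75/79 = 94.9%, 78/82 = 95.1%. Month 5: 60/79 = 75.95%, 59/82 = 71.95%, printed truncated as 75.9% and 71.9%. There is no arithmetic error here. (The itemised intervention reasons, 16 + 6 + 3 + 1, add to 26 rather than 27; the denominator of 79 implies 27, which is used below.)

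**2. Recompute from randomisation.** Differences are intervention minus control, with Wald 95% intervals, p₁ − p₂ ± 1.96·√[p₁(1−p₁)/n₁ + p₂(1−p₂)/n₂], and Fisher p-values.

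| | Intervention | Control | Difference in points (95% CI) | p |
|---|---|---|---|---|
| Early withdrawal | 27/106 = 25.5% | 4/86 = 4.7% | +20.8 (+11.4 to +30.2) | <0.001 |
| Retained, month 1 | 75/106 = 70.8% | 78/86 = 90.7% | −19.9 (−30.6 to −9.3) | 0.0006 |
| Retained, month 5 | 60/106 = 56.6% | 59/86 = 68.6% | −12.0 (−25.6 to +1.6) | 0.10 |
| Retained, month 5, as printed | 60/79 = 75.9% | 59/82 = 71.9% | +4.0 (−9.5 to +17.5) | 0.59 |

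**3. Does it depend on counting people found ineligible?** Removing those (6 and 2) leaves 100 and 84. Month 1 is 75/100 = 75.0% versus 78/84 = 92.9%; month 5 is 60/100 = 60.0% versus 59/84 = 70.2%. The pattern is the same.

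**4. Does it come from the change in allocation ratio?** Item 6 reports 27 and 3 early withdrawals as the reason for moving to 2:1. If those counts refer to the first 148, as the text reads, the loss was 27/75 = 36.0% versus 3/73 = 4.1% while allocation was 1:1. Pooling the two periods did not create the imbalance.

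**5. Planning figures.** n per arm = 2·[20·(1.96 + 0.84)/10]² = 62.8, rounded up to 63; 63/0.8 = 78.75, rounded up to 79, or 158 in all. Both reproduce. Realised retention is 119/192 = 62.0% of those randomised, with 60 and 59 seen at month 5.

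**6. Effect on power.**
- Completers only: SE = 20·√(1/60 + 1/59) = 3.67. Power is Φ(10/3.67 − 1.96) = 77.8%, or 77.2% by the t-test. The figures for 63 per arm are 80.1% and 79.5%.
- Planned mixed model: assume equal correlation ρ between visits, SD of change 20, and everyone seen at month 5 also seen at month 1. Per-arm variance of the mean change is 400·[(1 − R²)/n₅ + R²/n₁], where R² is the share of change variance explained by the baseline and month-1 values. At ρ = 0.5, R² = 1/3. The variances are 400·[(2/3)/60 + (1/3)/75] = 6.22 and 400·[(2/3)/59 + (1/3)/78] = 6.23. So SE = √12.45 = 3.53, and power = Φ(10/3.53 − 1.96) = 80.9%. It stays near 81% for ρ from 0.3 to 0.7.

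**The case against.** The best defence is openness. Item 20a states its restricted denominators and lists the early losses as percentages of those randomised. Item 6 says early withdrawal was higher in the intervention arm and changed the allocation because of it. Item 16b plans a propensity-adjusted analysis aimed at early withdrawals. The lack-of-bias sentence refers to withdrawal and follow-up data together, in a diagram that cannot be read in the text available here and may count from randomisation.

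The disclosure stands. It does not rescue item 20c: the fuller the data, the plainer the imbalance, since 27/106 against 4/86 cannot show lack of bias on any layout. Item 16b concerns estimation and does not make the sentence true; it also shows that the authors regard early withdrawal as needing adjustment.

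Three stronger readings are tempting, and the documents do not support them:

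- *The denominators hide the missed targets.* They do not. The printed 75.9% and 71.9% are already below 80%, and 60 and 59 are below 63 on any denominator.
- *The arm difference in month-5 retention is shown to run the other way.* Only the point estimate changes sign. Both intervals include zero. The firm contrasts are early withdrawal and month 1.
- *The trial lost its planned power, so item 7 must be rewritten.* The loss is about two points on completers and is roughly recovered by the planned model. Item 7 is a design-stage record, and 192 rather than 158 were randomised, partly to offset early loss.

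**Conclusion.** Item 20c is wrong as written. The SAP's own counts show early loss more than five times as frequent in the intervention arm (25.5% versus 4.7%), and a gap of about 20 points in month-1 retention from randomisation that the printed percentages do not show. At month 5 the gap is 12 points and compatible with no difference.

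This rests on the printed counts and on taking everyone randomised as the denominator; dropping those found ineligible does not change it. It does not show that the treatment effect is biased, or in which direction. It shows that balanced retention cannot be offered as evidence against bias. The shortfall against 63 per arm and 80% retention is real but minor for power, subject to the equal-correlation assumption for the mixed-model figure.

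**What to change.** - In item 20a, add retention at months 1 and 5 on all randomised (75/106 and 78/86; 60/106 and 59/86) beside the present figures, labelling the latter as conditional on not being an early withdrawal.
- In item 20c, replace the lack-of-bias sentence with one saying that early loss differed by arm, giving 27/106 and 4/86, and that attrition bias cannot be excluded.
- Leave item 7 as it is. At most, add a note that 60 and 59 were reached against 63 per arm and that 62% of those randomised were retained against 80% assumed, with power of about 77% by t-test on completers and about 81% under the mixed model with equal correlation.

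The cost is wording only. The stated retention becomes less favourable; no new data, participants or analyses are required.
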